Study Protocol and Statistical Analysis Plan

Official Title:

Evaluation of Observation Periods and Biphasic Reaction Risk Factors in Pediatric Anaphylaxis Cases in the Pediatric Emergency Department: A Retrospective Study

Brief Title:

Observation Periods and Biphasic Reaction Risk Factors in Pediatric Emergency Anaphylaxis Cases

Unique Protocol ID:

ADUPEDANAPH

NCT Number:**Responsible Party / Principal Investigator:**

Assoc. [name]. [name]

Department of Pediatrics (Emergency and Intensive Care)

Adnan Menderes University Faculty of Medicine, Aydın, Turkey

Co-Investigators:

- Dr. Öğr. Üyesi [name]
- Dr. Öğr. Üyesi [name]
- Uzm. [name] [name]

Ethics Approval:

Approved by the Clinical Research Ethics Committee of Adnan Menderes University Faculty of Medicine (Approval Date: 24/09/2025).

Document Date: 03 October 2025

1. Study Rationale

Anaphylaxis is a severe, rapidly developing systemic allergic reaction that poses unique challenges in pediatric emergency care. International guidelines recommend observation after treatment due to the risk of biphasic reactions (recurrence within 1–72 hours), but the optimal observation period in children is uncertain. Limited data exist from Turkey regarding pediatric anaphylaxis triggers, treatment practices, biphasic reaction frequency, and risk factors.

2. Objectives

- **Primary Objective:**

To determine the average observation period in the pediatric emergency department for children presenting with anaphylaxis and to evaluate the frequency and timing of biphasic reactions.

- **Secondary Objectives:**

- To analyze independent risk factors for biphasic reactions, including delayed epinephrine administration, asthma history, and severity at presentation.
- To assess the rate of hospital admission and need for intensive care.
- To describe treatment patterns (use and timing of epinephrine, corticosteroids, antihistamines, fluids) in the emergency setting.

3. Hypotheses

H1: Early administration of intramuscular epinephrine reduces the risk of biphasic reactions and improves clinical outcomes.

H2: A history of asthma and severe initial clinical presentation are associated with higher risk of biphasic reactions and prolonged observation requirements.

H3: Children requiring multiple doses of epinephrine are at increased risk for hospitalization and biphasic reactions.

4. Study Design

Type: Observational

Design: Retrospective analytic cohort (chart review)

Setting: Pediatric Emergency Department, Adnan Menderes University Hospital

Period: January 1, 2014 – December 31, 2024

Sample: All consecutive patients <18 years diagnosed with anaphylaxis

5. Study Population

Inclusion Criteria:

- Children aged 0–18 years
- Diagnosis of anaphylaxis according to WAO 2020 criteria
- Complete medical records available

Exclusion Criteria:

- Incomplete or missing medical records

- Cases not meeting WAO 2020 diagnostic definition
- Isolated urticaria or localized allergic reactions

6. Methods

Data Sources: Patient files and electronic medical records (January 2014 – December 2024).

Variables collected:

- Demographics (age, sex)
- Medical history (comorbidities such as asthma, allergic diseases)
- Triggers (food, drug, insect sting, idiopathic)
- Clinical manifestations (skin, respiratory, cardiovascular, gastrointestinal, neurological)
- Treatments (IM epinephrine, time to first dose, number of doses, IV antihistamines, IV corticosteroids, fluid therapy, inhaled therapy)
- Duration of ED observation, hospitalization, ICU stay
- Occurrence and timing of biphasic reactions
- Outcomes: discharge, readmission, mortality (if any)

7. Statistical Analysis Plan

- **Software:** SPSS v20.0
- **Descriptive statistics:** Continuous variables will first be tested for normality (e.g., Shapiro-Wilk test). Normally distributed variables will be presented as mean \pm SD, while non-normally distributed variables will be expressed as median (IQR). Categorical variables will be summarized as n (%).
- **Comparisons:** Chi-square or Fisher's exact test for categorical variables; Student's t-test or Mann-Whitney U test for continuous variables, depending on distribution.
- **Regression analysis:** Logistic regression to identify independent predictors of biphasic reactions and prolonged observation (candidate variables: time to epinephrine, asthma, severity, multiple epinephrine doses).
- **Significance level:** $p < 0.05$ considered statistically significant.

Sample size: All eligible patients.

8. Ethical Considerations

- Approved by Adnan Menderes University Faculty of Medicine Clinical Research Ethics Committee (Approval No: 2025/266).

- Retrospective study design → no informed consent required.
- All data anonymized and stored securely.

9. Expected Contribution

This study will provide evidence-based data for determining safe observation periods in pediatric anaphylaxis and will highlight risk factors for biphasic reactions in the Turkish pediatric population. Results are expected to guide clinical practice and support international guideline comparisons.

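### The second half of H1 names no outcome, and no severity-adjusted model links epinephrine timing to admission, ICU care or readmission

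*Combined protocol and SAP*

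**What the plan says.** Section 3 makes two claims in H1: "Early administration of intramuscular epinephrine reduces the risk of biphasic reactions and improves clinical outcomes". Biphasic reaction is named; what else should improve is not.

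Section 6 collects several quantities that could fill the gap: "Duration of ED observation, hospitalization, ICU stay", and separately "Outcomes: discharge, readmission, mortality (if any"). None is tied to H1 or ranked. Section 2 mentions admission and ICU need only as rates: "To assess the rate of hospital admission and need for intensive care". It does not connect them to epinephrine timing.

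Section 7 plans "Logistic regression to identify independent predictors of biphasic reactions and prolonged observation", with time to epinephrine, asthma, severity and multiple doses as candidate variables. For every other outcome the only comparison methods listed are "Chi-square or Fisher's exact test for categorical variables; Student's t-test or Mann-Whitney U test for continuous variables, depending on distribution". The threshold is 0.05. Sidedness and multiplicity are not addressed. Section 4 describes a retrospective chart-review cohort.

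**The concern.** H1 is worded causally, but timing of epinephrine was decided at the bedside, not assigned. The plan already treats severity as prognostic: H2 expects severe presentations to go with more biphasic reactions and longer observation, and severity is on the candidate list in Section 7. For admission, ICU care and readmission, which are natural readings of the second half of H1, no adjustment is planned. If severity also drives how soon a child is treated, a crude early-versus-late comparison mixes the effect of timing with the effect of being sicker.

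The second problem is choice. With no outcome named, this half of H1 could be declared supported by whichever quantity happens to favour early treatment.

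At stake is half of one hypothesis, not the primary objective. Section 9, however, expects the results to guide practice, so a biased statement about epinephrine timing would matter.

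**Working it through.** The plan gives no sample size, event rate or power, so there is no figure of its own to reproduce. Two illustrations show the possible size. Every rate below is assumed.

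**1. Confounding by severity**

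Inputs:
- 30% of children are severe.
- 50% of non-severe children are treated early.
- A share *e* of severe children is treated early.
- The true risk ratio for early treatment is 0.80 in both strata.
- Late-treatment admission risks are *s* (severe) and *m* (non-severe).

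Formulas:
- Early risk = (0.30·e·0.80·s + 0.35·0.80·m) / (0.30·e + 0.35)
- Late risk = (0.30·(1−e)·s + 0.35·m) / (0.30·(1−e) + 0.35)

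Example with s = 0.60, m = 0.15, e = 0.80:
- Early risk = (0.24·0.48 + 0.35·0.12)/0.59 = 0.1572/0.59 = 0.266.
- Late risk = (0.06·0.60 + 0.35·0.15)/0.41 = 0.0885/0.41 = 0.216.
- Crude risk ratio = 1.23.

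Example with s = 0.40, m = 0.20, e = 0.80:
- Early risk = (0.24·0.32 + 0.35·0.16)/0.59 = 0.1328/0.59 = 0.225.
- Late risk = (0.06·0.40 + 0.35·0.20)/0.41 = 0.0940/0.41 = 0.229.
- Crude risk ratio = 0.98.

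| Severe children treated early | Crude RR, risks 60% vs 15% | Crude RR, risks 40% vs 20% |
|---|---|---|
| 50% (no confounding) | 0.80 | 0.80 |
| 60% | 0.91 | 0.85 |
| 70% | 1.05 | 0.91 |
| 80% | 1.23 | 0.98 |
| 90% | 1.49 | 1.06 |

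The true effect is the same in both strata, so dividing the first column by 0.80 gives the crude ratio when there is no effect at all: 1.14 at 60% and 1.86 at 90%.

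A check on the odds-ratio scale behaves the same way. With a true odds ratio of 0.70, risks of 60% and 15%, and half of non-severe children treated early, the crude odds ratio is 0.75, 0.91 and 1.10 at 50%, 60% and 70% early use in severe children. The 0.75 at no confounding arises because odds ratios do not collapse over strata. With risks of 40% and 20% the values are 0.71, 0.78 and 0.85.

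**2. Choice of outcome**

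Five candidates are ED stay, hospitalization, ICU stay, readmission and mortality. H1 is directional, so only a favourable result supports it. At two-sided 0.05 (sidedness assumed) that has probability 0.025 per outcome when there is no effect and no bias. If the tests are independent:
- five outcomes: 1 − 0.975^5 = 0.119, about 12%;
- three outcomes: 1 − 0.975^3 = 0.073, about 7%.

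Counting both directions, five outcomes give 1 − 0.95^5 = 0.226, but an unfavourable result would not be claimed as support for H1.

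**The case against.** Much can be said for the plan.

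- **Confounding is assumed.** Nothing in the documents says that sicker children are treated sooner or gives admission risks by severity. This stands. Reversal needs severity to be strongly linked to both timing and admission; with a twofold risk gap the crude ratio stays below 1 up to 80% early use.
- **The two harms pull against each other.** If confounding makes early treatment look worse, falsely favourable results become rarer than 2.5% per outcome. The candidates are also correlated, since ED stay, hospitalization and ICU stay lie on one care pathway, and deaths may be too few to test. This stands, and makes 12% an upper figure.
- **Prolonged observation is already modelled with severity.** It is arguably a clinical outcome. But H1 does not cite it, no cut-off is given, and being a candidate does not guarantee that severity stays in the model. It does not cover admission, ICU care or readmission.
- **Overlap with H3.** H3 names hospitalization, also without a model. One admission regression can largely serve both hypotheses, so the overlap is real. What remains specific to H1 is the unnamed outcome and the timing estimate.
- **Adjustment can mislead.** If time to first dose runs from symptom onset, severity at presentation may partly result from delay, and adjusting would remove part of the effect. Section 6 gives neither a time origin nor a severity grading. This stands, and the fix has to deal with it.

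**Conclusion.** The gap is real and worth closing, but moderate. The second half of H1 has no stated outcome. The only methods listed that could link timing to admission, ICU care or readmission are unadjusted.

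If sicker children are treated sooner, those tests understate a benefit. Under the assumptions above, a true risk ratio of 0.80 would appear as 0.91 to 1.49 with a fourfold admission-risk gap and 60–90% early use in severe children. With a twofold gap it would appear as 0.91, 0.98 and 1.06 at 70%, 80% and 90%. Free choice among five independent outcomes gives up to a 12% chance of at least one false favourable result, and less with correlated outcomes or with confounding against early treatment.

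Three stronger readings are not supported:
- A reader might infer that the study will find the wrong sign. The documents give no rates, so reversal is only a possibility under strong confounding.
- A reader might infer a 23% false-positive risk for H1. That figure counts results in both directions.
- A reader might infer that H1 has no outcome at all, or that severity is ignored throughout. Biphasic reaction is named, and severity is a candidate in both planned models.

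**What to change.** 1. **Section 3, before abstraction:** name the outcome for the second half of H1. Hospital admission is a reasonable choice, because hospitalization is already collected and appears in the objectives and in H3. Label ICU care, readmission and death descriptive.
2. **Section 7:** add hospital admission as a third logistic-regression outcome, with time to epinephrine as the exposure and severity and asthma forced in. Base this half of H1 on the adjusted odds ratio and its 95% CI.
3. **H3:** the same regression extended with multiple doses can serve H3. Report the H1 timing estimate from the model without dose count, because later doses follow the first.
4. **Definitions:** state whether time to first dose runs from symptom onset or ED arrival, how severity is derived from the recorded manifestations, and how children given no epinephrine are handled. If time runs from onset, also report the estimate without severity.
5. **If admissions are too few for a model:** delete the second half of H1 or label it exploratory, and draw no H1 conclusion from crude tests.

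The cost is some SAP wording and one extra regression on data that are mostly collected already. The sponsor also gives up the option of claiming H1 from an outcome chosen later.

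### H3 predicts more hospitalization after multiple epinephrine doses, but the SAP plans no adjusted analysis of admission, so a crude comparison that severity can confound is the most this half receives

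*Combined protocol and SAP*

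**What the plan says.** Section 3 (Hypotheses) gives H3 one exposure and two outcomes: "Children requiring multiple doses of epinephrine are at increased risk for hospitalization and biphasic reactions".

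Section 7 (Statistical Analysis Plan) plans "Logistic regression to identify independent predictors of biphasic reactions and prolonged observation", with "candidate variables: time to epinephrine, asthma, severity, multiple epinephrine doses". Hospital admission is not among the outcomes. For other yes/no comparisons the same section offers "Chi-square or Fisher's exact test for categorical variables", without naming the outcomes or groups to be compared.

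Admission appears in two other places. A secondary objective in section 2 is "To assess the rate of hospital admission and need for intensive care", which is descriptive. The collected variables in section 6 include "Duration of ED observation, hospitalization, ICU stay". The separate outcome item in section 6 names discharge, readmission and mortality. The secondary objective on independent risk factors concerns biphasic reactions only.

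**The concern.** H3 is one hypothesis, but its two halves are analysed differently. For biphasic reactions, the model can hold severity alongside multiple doses. For hospitalization, no model is planned, and the only method that fits is an unadjusted test.

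Severity is the obvious confounder. A child who is sicker at presentation plausibly receives more doses and is more likely to be admitted, whether or not repeat dosing carries information of its own. The plan already treats severity as relevant: H2 links severe presentation to biphasic reactions and prolonged observation, and the SAP makes severity a candidate variable.

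At stake is the reading of a significant result. If the report gives an adjusted odds ratio for biphasic reactions and a crude p-value for hospitalization under the same hypothesis, readers may take both as evidence beyond severity. The second would not be. Section 9 expects the results to guide practice.

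**Working it through.** **Step 1: compare outcomes.** The plan states no figure on this point, so there is nothing to reproduce. The check begins with the text.

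- H3 outcomes: hospitalization; biphasic reactions.
- Regression outcomes: biphasic reactions; prolonged observation.
- Overlap: biphasic reactions only.

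Prolonged observation cannot stand in for admission. Section 6 lists ED observation and hospitalization as separate items, and prolonged observation is not defined.

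**Step 2: can severity alone produce the crude association?** All inputs here are assumed; none comes from the documents. Let s be the share of severe cases, m1 and m0 the probability of multiple doses in severe and other cases, and a1 and a0 the probability of admission in severe and other cases. Admission depends on severity only, so the odds ratio within each stratum is 1.

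- P(multiple) = s·m1 + (1−s)·m0
- Severe share among multiple-dose children: s·m1 / P(multiple)
- Severe share among the rest: s·(1−m1) / (1−P(multiple))
- Admission in each group: (severe share)·a1 + (1 − severe share)·a0

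Strong case, s = 0.4, m1 = 0.5, m0 = 0.1, a1 = 0.6, a0 = 0.1:

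- P(multiple) = 0.20 + 0.06 = 0.26
- Severe shares: 0.20/0.26 = 0.769 and 0.20/0.74 = 0.270
- Admission: 0.769·0.6 + 0.231·0.1 = 0.485, and 0.270·0.6 + 0.730·0.1 = 0.235
- Crude odds ratio: (0.485/0.515) / (0.235/0.765) = 3.06 (from unrounded values)

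The same formulas give:

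| Case | s | m1, m0 | a1, a0 | Admitted, multiple vs not | Crude OR |
|---|---|---|---|---|---|
| Weak | 0.2 | 0.2, 0.1 | 0.5, 0.3 | 36.7% vs 33.6% | 1.14 |
| Middle | 0.3 | 0.4, 0.1 | 0.5, 0.1 | 35.3% vs 18.9% | 2.34 |
| Strong | 0.4 | 0.5, 0.1 | 0.6, 0.1 | 48.5% vs 23.5% | 3.06 |

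Two grids of assumed inputs gave 1.14 to 2.80 (milder links) and 1.69 to 3.24 (stronger links). Together they span about 1.1 to 3.2.

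**Step 3: how often would the crude test favour H3 falsely?** The documents give no sample size, so the totals are also assumed.

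- Weak case, normal approximation for two proportions, counting significance in the H3 direction only (nominal 2.5%): 4.2%, 5.0% and 6.4% with 100, 200 and 400 children.
- Middle case, 2,000 simulated studies per setting, p < 0.05 in either direction (nominal 5%): 31.8% with 100 children and 58.9% with 200. A logistic model with multiple doses and severity gave 4.2% and 4.6%.
- Strong case, same simulation: 65.9% and 90.5% crude; 5.8% and 4.3% adjusted.

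The adjusted figures assume that severity is binary and recorded without error, which flatters the model.

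**The case against.** The strongest objection is that H3 says only that risk is increased. It does not claim an independent effect; the plan uses that word for biphasic reactions in the objectives and for the two regression outcomes. A crude comparison therefore answers the hospitalization half of H3 as written. This stands: the crude test is legitimate for a risk-marker statement. But the biphasic half is worded identically and does get a model for independent predictors, so the difference in treatment is the plan's own. Labelling the crude result unadjusted would prevent misreading, but would still leave unanswered whether the association goes beyond severity.

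Two further objections limit the point. Severity and multiple doses are only candidate variables and no selection rule is given, so adjustment of the biphasic half is possible, not assured. Nor does the SAP expressly assign the chi-square or Fisher's test to admission by number of doses; that test is simply the most the plan offers.

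A reader might infer that the planned comparison is bound to give a spurious result. The documents do not support that: with weak links between severity, dosing and admission, the distortion is small. A reader might also infer that admission is not captured because it is missing from the outcome item in section 6. The admission-rate objective and the hospitalization data show that admission yes/no can be derived. Finally, a reader might infer that admitted children bias the average ED observation time or the prolonged-observation outcome. The documents do not say when ED time ends for an admitted child or what counts as prolonged, so no direction follows and this point makes no such claim.

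**Conclusion.** The mismatch is confirmed from the text: H3 names hospitalization, no adjusted analysis of it is planned, and the most it receives is an unadjusted comparison. Such a comparison cannot separate multiple doses from severity.

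The size is not known from the documents. In the assumed settings the distortion favours H3, but it ranges from slight (odds ratio about 1.1) to large (about 3.2). These figures show what severity could do, not what it will do in this cohort. They assume that severe cases more often receive multiple doses and are more often admitted.

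The point concerns half of one hypothesis and does not touch the estimate of biphasic reaction frequency. It merits a change before analysis because the remedy is cheap.

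**What to change.** In section 7:

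- Add hospital admission (yes/no, derived from the hospitalization data) as a third logistic regression outcome, with multiple doses and severity as covariates.
- Define one severity grading from the recorded clinical manifestations, fix it before analysis, and use it in all models.
- If admissions are too few for the model, give a Mantel-Haenszel odds ratio for multiple doses stratified by severity.
- Report the crude result beside the adjusted one, labelled unadjusted.

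No new data collection is implied. Number of doses, hospitalization and manifestations by organ system are already listed in section 6. Severity is named as a candidate variable but has no stated grade, so writing that definition is the main extra work.

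There are two downsides. The estimate will be imprecise if admissions are few: in the simulations, the median ratio of upper to lower 95% confidence limit was about 11 to 24 with 16 to 30 admissions, and about 5 to 9 with 32 to 60. Residual confounding will also remain if severity is graded coarsely, so the adjusted result should be described as adjusted for recorded severity only.

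### Eleven years of cases are pooled and visit year is neither collected nor analysed, so a calendar trend could be neither seen nor adjusted for

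*Combined protocol and SAP*

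**What the plan says.** Section 4 describes a single-department retrospective chart review, with "Period: January 1, 2014 – December 31, 2024" and the sample given as "All consecutive patients <18 years diagnosed with anaphylaxis". Section 5 applies one case definition to every year, as an inclusion criterion ("Diagnosis of anaphylaxis according to WAO 2020 criteria") and again as an exclusion ("Cases not meeting WAO 2020 diagnostic definition"). No codes, search terms or screening procedure are given for finding the charts.

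The primary objective in Section 2 is "To determine the average observation period in the pediatric emergency department for children presenting with anaphylaxis", together with how often and when biphasic reactions occur. H1 in Section 3 is worded causally: "Early administration of intramuscular epinephrine reduces the risk of biphasic reactions and improves clinical outcomes".

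Section 6 lists durations and timings within a visit but no date or year of the visit. Section 7 plans pooled summaries, two-group comparisons and logistic regression with "candidate variables: time to epinephrine, asthma, severity, multiple epinephrine doses". It has no calendar term, no results by period and no sensitivity analysis. Section 8 says the data will be anonymised. Section 9 expects the results to help set safe observation periods and to inform practice.

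**The concern.** Eleven years is long enough for recognition, treatment speed, length of stay and record-keeping to change in a department. Two things follow if they did.

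First, H1 compares children treated earlier with children treated later. If epinephrine came sooner in one part of the window, and biphasic reactions were also more or less common (or better recorded) in that part, time to epinephrine becomes partly a marker of calendar year. None of the four candidate variables is calendar time, so the planned model has no direct way to separate the two.

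Second, one average over 2014–2024 may match neither the early nor the recent years. That matters if the figure is read as a guide to present observation practice.

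There is also a practical point. Confirming that a visit falls in the window requires its date, so year is available when the chart is read. Because year is not a listed variable and the data are then anonymised, it may not be recoverable later.

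**Working it through.** **Plan's own figures.** The documents give no cohort size, event rate or effect size, so there is nothing to reproduce except the window. From 1 January 2014 to 31 December 2024 is 11 calendar years, of which 6 (2014–2019) precede 2020.

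**Confounding of H1: set-up.** Take two periods, 2014–2019 and 2020–2024, with equal cases per year, so the weights are w1 = 6/11 and w2 = 5/11. Let d1, d2 be the proportions with delayed epinephrine and b1, b2 the biphasic risks. Within each period the risk is the same for delayed and non-delayed children, so the true odds ratio is 1.00. All d, b and w values are assumptions.

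- Risk if delayed: rD = (w1·d1·b1 + w2·d2·b2) / (w1·d1 + w2·d2)
- Risk if not delayed: rN = (w1·(1−d1)·b1 + w2·(1−d2)·b2) / (w1·(1−d1) + w2·(1−d2))
- Pooled odds ratio for delay: [rD/(1−rD)] / [rN/(1−rN)]

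Worked case, with weights multiplied by 11 (delayed 60% then 25%, biphasic 3% then 6%):

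- rD = (6×0.60×0.03 + 5×0.25×0.06) / (6×0.60 + 5×0.25) = 0.183/4.85 = 3.77%
- rN = (6×0.40×0.03 + 5×0.75×0.06) / (6×0.40 + 5×0.75) = 0.297/6.15 = 4.83%
- Odds ratio = 0.77

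| Delayed, early → late | Biphasic, early → late | rD | rN | Pooled OR for delay |
|---|---|---|---|---|
| 60% → 25% | 3% → 6% | 3.77% | 4.83% | 0.77 |
| 60% → 25% | 6% → 3% | 5.23% | 4.17% | 1.27 |
| 50% → 30% | 4% → 6% | 4.67% | 5.08% | 0.92 |

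H1 predicts a value above 1. The first row would count falsely against it and the second falsely for it.

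**Sensitivity to the inputs.** A separate grid was expressed as the odds ratio for early rather than delayed epinephrine. It took early treatment at 50% in both periods or rising to as much as from 30% to 80%, biphasic risk from unchanged at 5% to falling from 10% to 3% or rising from 4% to 8%, and w1 of 6/11 or 0.35. Pooled values ran from 0.53 to 1.45. Whenever either factor was held constant, the result was exactly 1.00.

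**Size against sampling error.** Take the 0.77 case and an assumed 200 children. The delayed share is 4.85/11 = 44.1%, giving 88.2 delayed children with 3.33 expected events and 111.8 others with 5.40, about 9 events in all. The standard error of the log odds ratio is √(1/3.33 + 1/84.9 + 1/5.40 + 1/106.4) = 0.71. The expected 95% interval is exp(−0.258 ± 1.96×0.71), or 0.19 to 3.1. The chance of two-sided p < 0.05 with no true effect is then about 7%. It is about 9% with 500 children and 13% with 1,000. In the 0.92 case it stays at 5–6%.

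**Primary average.** The pooled mean is w1·m1 + w2·m2. Assumed period means of 12 h and 8 h give (6×12 + 5×8)/11 = 10.2 h with equal cases per year, or 0.35×12 + 0.65×8 = 9.4 h if 35% of cases are early. The pooled figure depends on how cases fall across years and need not equal either period's mean.

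**The case against.** The best defence is that this is a general limitation of long retrospective cohorts and that nothing in the documents shows a trend at this site. That stands. Confounding of H1 by calendar time needs drift in both epinephrine timing and biphasic risk or its recording, and drift in only one gives no bias. The odds ratios above are crude, whereas the plan adjusts for asthma, severity and number of doses. In a cohort of a few hundred, sampling error would far exceed the bias illustrated. A reader might infer that a time trend alone could settle H1. On these inputs it shifts the estimate but raises the false-positive rate only modestly.

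A reader might also infer that children seen before 2020 are under-represented, because clinicians could not then have used 2020 criteria and a retrospective filter cannot add cases charted as something else. The documents do not support this as fact. The sample line suggests a start from charted diagnoses, but the search is not described. The exclusion of isolated urticaria and localised reactions would also fit a wider search. Nothing shows that recognition differed by period, or that unrecognised children were treated later. Applying one definition to all years is also partly a safeguard, since it removes over-labelled cases throughout.

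Finally, a fifth term in the main model could be costly if biphasic events are few. That also stands, and it shapes the fix.

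**Conclusion.** The point holds as a gap in the plan, not as a demonstrated bias. Visit year is absent from data collection, description and modelling, so the study as written could not show whether practice changed or whether H1 survives allowance for calendar time. Under assumed inputs with no true effect, the crude odds ratio for delay moves to about 0.92 with mild drift and to 0.77 or 1.27 with stronger drift.

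It would go too far to call the primary average distorted. It correctly summarises 2014–2024 for the cases found. The reservation is about using it as a guide to recent practice. The change is worth making because it is cheap and because year may be lost once the data are anonymised.

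**What to change.** 1. Add year of presentation to the Section 6 variables and keep it in the anonymised dataset.
2. Report ED observation time and the frequency and timing of biphasic reactions for 2014–2019 and 2020–2024 beside the pooled result. The split follows the year of the case definition, not a known change in practice, and the report should say so.
3. Repeat the time-to-epinephrine model for biphasic reactions with year as a single linear term, as a prespecified sensitivity analysis. Move it to the main model only if the number of biphasic events allows.
4. Describe how charts were found, and report possible under-capture of earlier cases as a limitation.

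The cost is one extra field per chart, using a date the window already requires, a few table columns and one further model run. The downsides are smaller numbers per period, hence wider intervals, and one more parameter in the sensitivity model. A linear term will also capture an abrupt change only approximately. Widening the chart search to other allergic diagnoses would be extra work resting on an inference about the search, and is not needed for this fix.

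### The sampling rule admits children who reach this ED only because a reaction treated elsewhere has recurred, and no planned variable identifies them

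*Combined protocol and SAP*

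**What the plan says.** The primary objective in Section 2 includes an aim "to evaluate the frequency and timing of biphasic reactions". Section 1 describes "biphasic reactions (recurrence within 1–72 hours" as the window, without saying when the clock starts.

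Section 4 gives the setting as one department ("Setting: Pediatric Emergency Department, Adnan Menderes University Hospital") and the sample as "All consecutive patients <18 years diagnosed with anaphylaxis". Section 5 adds age, "Diagnosis of anaphylaxis according to WAO 2020 criteria" and completeness of the chart, and it excludes "Incomplete or missing medical records". It does not define the index reaction or say where first treatment must have taken place.

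The outcome item in Section 6 is "Occurrence and timing of biphasic reactions". The same list has time to first epinephrine and number of doses, but nothing on referral source or on treatment at another facility before the visit. The data sources are patient files and electronic records. No follow-up contact or linkage to other hospitals is described.

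**The concern.** Biphasic frequency is a risk: children who recur, divided by children who had a first reaction and could have recurred. That reading requires entry to the cohort to be independent of recurrence. For a child treated and released elsewhere, entry here depends on recurrence. Such a child adds one to the numerator and one to the denominator, while children released elsewhere who stayed well have no reason to attend this ED.

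Three results are exposed:

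- **Frequency.** Both coding choices distort it, in opposite directions. Counting the child as biphasic inflates it. Coding the visit as a new index reaction turns a true recurrence into a non-event.
- **Timing.** Only events contribute, so a few entrants carry a lot of weight. Their recurrences happened after leaving one facility and reaching another, so long intervals are likely.
- **H1–H3 models.** Time to epinephrine and multiple doses are candidate predictors in Section 7. For a child arriving in recurrence, epinephrine recorded in this ED treats the outcome. Severity recorded on arrival is, likewise, the severity of the recurrence.

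Section 9 expects the results to inform safe observation periods, so errors in frequency and timing bear directly on the intended use. A larger sample does not remove this kind of error, and with the planned variables it could be neither detected nor corrected afterwards.

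**Working it through.** The plan states no sample size, expected event count or biphasic rate, so there is no figure to reproduce. Every number below is an assumption chosen to show scale.

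**Inputs (assumed).** 200 children first treated here, 10 true recurrences (5.0%); e = children entering only through recurrence, set to 2, 4 or 6; m = share of this ED's own recurrences that its records do not capture.

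**1. Entrants counted as biphasic, m = 0.** Observed frequency = (10 + e)/(200 + e); entrants' share of timed events = e/(10 + e).

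| e | Frequency | Share of timed events |
|---|---|---|
| 2 | 12/202 = 5.9% | 2/12 = 17% |
| 4 | 14/204 = 6.9% | 4/14 = 29% |
| 6 | 16/206 = 7.8% | 6/16 = 38% |

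With e = 0 there is no effect.

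**2. Entrants coded as new index reactions without a second phase, m = 0.** Observed frequency = 10/(200 + e): 10/202 = 4.95%, 10/204 = 4.90%, 10/206 = 4.85%. This is a small dilution, and the true recurrences add nothing to timing.

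**3. Entrants counted as biphasic, half of own recurrences unseen (m = 0.5).** Observed frequency = (5 + e)/(200 + e): 7/202 = 3.5%, 9/204 = 4.4%, 11/206 = 5.3%. Two of the three fall below the true 5.0%.

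**4. Break-even.** Setting (10(1 − m) + e)/(200 + e) = 0.05 gives e = 10m/0.95. That is 2.6 entrants at m = 0.25 and 5.3 at m = 0.5. Above this number the net error is upward; below it, downward.

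**5. Timing.** Assume that of the 10 own recurrences, 6 occur at a mean of 4 h and 4 at 24 h, and that entrants recur at 24 h.

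- No entrants: (6×4 + 4×24)/10 = 12.0 h.
- e = 2: (120 + 48)/12 = 14.0 h.
- e = 4: (120 + 96)/14 = 15.4 h.
- e = 6: (120 + 144)/16 = 16.5 h.
- No entrants, but half of the 24 h recurrences unseen: (24 + 48)/8 = 9.0 h.

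**6. Effect of the fix.** Removing the entrants returns 10/200 = 5.0% when m = 0. When m > 0 it leaves 5.0% × (1 − m), for example 3.75% at m = 0.25. It removes the error due to entry at recurrence but does not recover recurrences missed elsewhere.

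**The case against.** A reader might infer that the primary frequency will be too high and its timing too late. The documents do not support that, for five reasons:

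- **No coding rule.** Section 6 does not say how such a visit is charted. Coded as an index reaction, it lowers frequency slightly.
- **No count.** The documents do not mention children arriving in recurrence from other facilities. That they exist is an inference from the university-hospital setting, and there may be none.
- **An opposing error.** Children first treated here who recur elsewhere may not appear in this hospital's records. That lowers frequency and removes late events, and it can outweigh the entrants (steps 3 to 5).
- **A criterion that may remove some.** A child whose first phase was treated elsewhere may count as having an incomplete chart. Section 5 does not say whether a missing outside record has that effect.
- **Some treated elsewhere do enter without recurrence.** The same sampling rule admits children transferred here during their first phase, so it would be wrong to say that non-recurring children treated elsewhere never appear.

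All five stand as limits on the claim of direction and size. None closes the gap. The opposing error is separate and also of unknown size, and there is no reason to expect the two to cancel. Any screening through chart completeness would be incidental and undocumented. Transfers do not stand in for children sent home well from other facilities.

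**Conclusion.** The point holds in conditional form. Under Sections 4 to 6 as written, a child who arrives in a qualifying recurrence of a reaction treated elsewhere is eligible and cannot be recognised in the planned dataset. If counted as biphasic, that child has entered because of the outcome. This component can only raise frequency, probably makes timing later, and places treatment of the outcome among the predictors in the H1 and H3 models. If coded as a new index reaction, a true recurrence is lost.

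The range of 5.9% to 7.8% against 5.0% rests on the assumed 10/200, on 2 to 6 entrants, on their being counted as biphasic, and on no missed recurrences. The real number of such children and the net direction of bias are unknown. A firm statement that the study will overestimate biphasic risk would go beyond the documents, and nothing here shows an effect on the average observation period, the other half of the primary objective.

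The plan should still be changed: the flaw lies in the stated sampling rule, it touches a primary result, and it is cheap to repair before chart abstraction.

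**What to change.** Add one chart item to Section 6: *this visit is for recurrence of a reaction already treated at another facility before arrival here (yes/no)*. Add one sentence to Section 5 stating how the item is used:

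- Leave only the children coded yes out of the numerator and denominator of the primary biphasic frequency, the timing analysis and the H1–H3 models.
- List them separately, and report frequency, timing and the models with and without them.
- Keep children transferred here during their first phase, and children given epinephrine before arrival at home or by ambulance. They did not enter because of a recurrence. Dropping the pre-arrival epinephrine group would also remove early-treated children, whose exposure H1 is about.

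The cost is one extra field per chart and somewhat fewer biphasic events for the models. Recurrences of this ED's own patients seen elsewhere remain uncaptured and should be reported as a limitation.
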